6.3 Statistical Analysis

We will perform intention-to-treat analysis to analyze outcomes of all enrolled patients. The primary analysis is to evaluate the CRF or disease progression rate against the null proportion. We plan to perform two interim analyses and one final analysis. The first interim analysis will be performed after enrolling and observing outcomes of one-third of maximum sample size. At an interim analysis, CRF or disease progression rate will be reported, together with a score confidence interval for the rate. The critical value used to evaluate the confidence interval is 2.289 based on the Pocock method. We will compare the upper limit of the confidence interval with the assumed null proportion. We will conclude efficacy of the treatment if the upper limit is less than the null proportion and terminate enrollment for the relevant study group. If the upper limit is greater than the null proportion, we will proceed to the second stage of enrollment and then perform the second interim analysis on the cumulative data. The same evaluation will be replicated in the second interim analysis, as well as in the final analysis should we proceed to this step.

After completing the trial, we will conduct secondary analysis to compare outcomes of this trial with published historical experience. We will use the score test for comparing two proportions in each evaluation. We will report both p value and 95% score confidence interval for difference between two proportions.

It is acknowledged that COVID-19 viral pandemic outbreak remains dynamic. Epidemiological update reports from the CDC may result in reassessment for case fatality rates as well as case rates for disease progression used in our study design that may require adjustments in sample size determinations at the interim analysis as independently allowed by the biostatistician.

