that the correct product was infused. Risk of infectious disease transmission is extremely low due to FDA required extensive donor medical screening and infectious disease testing. The estimated risk for acquiring HIV, HCV and HBV through transfusion is 1:1,467,000, 1:1,149,000 and 1:280,000 donations, respectively.

Hypothetical concerns regarding the use of convalescent plasma include the phenomenon of antibody-dependent enhancement of infection (ADE). For coronaviruses, several mechanisms for ADE have been described and there is the theoretical concern that antibodies to one type of coronavirus could enhance infection to another viral strain.xiv Because convalescent plasma will have titers of neutralizing antibody against COVID-19, ADE is not anticipated to develop. The anecdotal report of the use of convalescent sera in patients with SARS1 and MERS, and evidence from its use in 245 patients with COVID-19 acute infection suggest it is safe and has not resulted in ADE. Another hypothetical concern is that the use of convalescent plasma may suppress the hosts humoral immune response, thereby, leaving the patient vulnerable to subsequent reinfection. There is no data to substantiate this concern in prior use of convalescent plasma for coronavirus diseases. There is also the risk that convalescent plasma for COVID-19 infection may be ineffective.

The potential benefits of administering convalescent plasma have been outlined in Section 1.1. The infusion of convalescent plasma will likely provide immediate passive neutralizing antibodies against the virus. Historical observations for other viral pandemic infections have demonstrated lower risk for morbidity and mortality. Investigators have shown correlation of rapid reversal of inflammatory response to the infection and cytokines following infusion of convalescent plasma for the SARS Coronavirus. In the recent report from China, 245 patients were given convalescent plasma and it was concluded that approximately 35% showed clinical benefit. It is hoped that the administration of convalescent plasma to the study patients will reduce the severity and duration of the infection, and the risk for death.

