6.0 Statistical and Quantitative Analysis

6.1 Determination of Sample Size and Statistical Analysis

Group sequential design is employed for each hypothesis that analysis will be performed after enrolling and observing outcomes of one-third of maximum sample size. Our design includes two interim analyses and a final analysis for each hypothesis. The Pocock method is used to determine sample size and each study is sized to maintain the power of 80% and overall type I error 5%. To calculate the sample size, the large-sample Z test for a proportion is utilized for each analysis.

	Enrollment at stage 1	Enrollment at stage 2	Enrollment at stage 3	Maximum enrollment	Expected enrollment for projected proportion
Study group 3	76	76	76	228	159
Study group 4	73	73	73	219	152

Group 3

For high-risk COVID-19 infected patients that present with early mild or non-severe disease the estimated percent who will develop severe disease is 27% for those over age 65. There is insufficient data on patients who have coexisting severe immune compromised status; however, for patients that presented with diabetes or heart disease/hypertension risk was 16% - 30%, respectively. Assuming a reported risk of progression of 25%, it is postulated that the infusion of convalescent plasma will reduce the probability for progression to severe disease by a factor of 0.35 to 16.3% or lower. We will carry out 3-stage of enrollment and 76 patients are enrolled in each stage. The interim analysis will be performed after enrolling and observing outcomes of 76 patients. Our design leads to the maximum size of 219 patients after completing 3-stage of enrollment and the expected size is 159 patients.

Group 4

Among healthcare workers 14.8% of cases were classified as evolving to severe or critical per the Chinese epidemiological review. ^{24,25} It is postulated that the infusion of convalescent plasma will reduce the probability for progression from asymptomatic, mild or nonsevere disease to that of severe disease will be reduced by a factor of .5 to 7.5% or lower. We will carry out 3-stage of enrollment and 73 patients are enrolled in each stage. The interim analysis will be performed after enrolling and observing outcomes of 73 patients. Our design leads to the maximum size of 219 patients after completing 3-stage of enrollment and the expected size is 152 patients.

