8.7 Closure of the Study

This study may be prematurely terminated, if in the opinion of the investigator there is sufficient reasonable cause.

Circumstances that may warrant termination include, but are not limited to:

- Determination of unexpected, significant, or unacceptable risk to patients
- Failure to enter patients at an acceptable rate
- Insufficient adherence to protocol requirements
- Insufficient, incomplete and/or unevaluable data
- Determination of efficacy based on interim analysis

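### The interim rule in Section 6.3 acts only on the upper confidence limit, so an interval wholly above the null prompts no review before the next stage opens

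*Combined protocol and SAP*

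**What the plan says.** Section 6.3 reports the progression rate at each interim "together with a score confidence interval for the rate". On the constant it says: "The critical value used to evaluate the confidence interval is 2.289 based on the Pocock method". Two outcomes are then defined, both by the upper limit:

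- Upper limit below the null: "We will conclude efficacy of the treatment if the upper limit is less than the null proportion and terminate enrollment for the relevant study group".
- Upper limit above the null: "If the upper limit is greater than the null proportion, we will proceed to the second stage of enrollment".

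For the later looks: "The same evaluation will be replicated in the second interim analysis, as well as in the final analysis". No action is attached to the lower limit, and the document describes no harm boundary, futility boundary or data monitoring board. The last paragraph of 6.3 allows sample-size adjustment when epidemiological rates are updated, which is a different matter.

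Section 8.7 lets the investigator end the study early for reasonable cause. Its open-ended list includes "Determination of unexpected, significant, or unacceptable risk to patients". The one item on that list that mentions the interim analysis concerns efficacy. Section 7.1.1 restricts adverse event capture to events at least possibly related to the infusion, and Section 7.2 restricts serious event reporting to events that the treating physician judges potentially related.

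**The concern.** The constant 2.289 gives an interval with about 2.5% error on each side over three looks. The plan spends one side on efficacy and leaves the other unused. A first look with 30 progressions in 76 and one with 15 in 76 receive the same written instruction.

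This matters because there is no control arm, and the other safety channel may not see excess progression. Section 1.5 lists antibody-dependent enhancement as a hypothetical risk and concedes that a respiratory change after infusion will be hard to attribute to the plasma. A patient whose worsening is put down to COVID-19 falls outside the capture rule in 7.1.1 and the reporting rule in 7.2. The pooled progression rate is where such an excess would show, and the plan gives that finding no consequence. What is at stake is whether one or two further stages (76 patients each in Group 3, 73 in Group 4) open without anyone being required to look at it.

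**Working it through.** **Inputs.** From Section 6.1: Group 3 null 25%, target 16.3%, stages of 76; Group 4 null 14.8%, target 7.5%, stages of 73; power 80%, overall type I error 5%. From Section 6.3: score interval, c = 2.289. For the Group 3 maximum I use 3 × 76 = 228, as in the table; the text of 6.1 says 219.

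**1. Reproduce the plan's design.** Fixed-sample size is p0(1 − p0)(1.96 + 0.84)² / (p0 − p1)², multiplied by the three-look Pocock inflation of 1.166 and rounded up to three equal stages.

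- Group 3: 194.4 × 1.166 = 226.7, giving 3 × 76 = 228. Expected size under the normal approximation is 159.6 (plan: 159).
- Group 4: 185.7 × 1.166 = 216.6, giving 3 × 73 = 219. Expected size is 153.0 (plan: 152).
- c = 2.289 over three looks gives 0.0502 two-sided, about 0.025 per side. One-sided 5% sizing does not reproduce the plan (at most 184 and 176).

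**2. When does the interval exclude the null?** The score interval excludes p0 exactly when |x − n·p0| > 2.289 × √(n·p0(1 − p0)).

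| Look | n·p0 | Half-width | Efficacy (upper limit < null) | Lower limit > null | Interval at that count |
|---|---|---|---|---|---|
| G3, n = 76 | 19.00 | 8.64 | x ≤ 10 | x ≥ 28 (36.8%) | 25.4% to 50.0% |
| G3, n = 152 | 38.00 | 12.22 | x ≤ 25 | x ≥ 51 (33.6%) | 25.5% to 42.7% |
| G4, n = 73 | 10.80 | 6.94 | x ≤ 3 | x ≥ 18 (24.7%) | 15.1% to 37.6% |
| G4, n = 146 | 21.61 | 9.82 | x ≤ 11 | x ≥ 32 (21.9%) | 15.1% to 30.7% |

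The final efficacy bounds are x ≤ 42 of 228 and x ≤ 20 of 219. For illustration, 30/76 gives 27.7% to 52.6% and 15/76 gives 11.4% to 32.0%. In both the upper limit exceeds 25%, so the written action is to proceed.

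**3. Effect on the efficacy test.** With exact binomial recursion, power at the target is 84.8% (Group 3) and 86.4% (Group 4), and efficacy type I error is 2.2% and 1.4%. These are the same whether or not a crossing of the lower limit stops enrolment.

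**4. How often the trigger fires, and the most it could save.** The true rates are assumptions. The last column treats every firing as the end of enrolment, so it is a best case.

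| Group, true rate | Fires at look 1 | Fires by look 2 | Expected N as written | Expected N, best case |
|---|---|---|---|---|
| G3, 30% | 12.1% | 23.3% | 228 | 201 |
| G3, 35% | 41.0% | 70.6% | 228 | 143 |
| G3, 40% | 75.0% | 96.3% | 228 | 98 |
| G4, 25% | 57.2% | 85.1% | 219 | 115 |
| G4, 30% | 87.1% | 99.0% | 219 | 83 |

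For Group 3 at 40%: 76 × 0.7500 + 152 × 0.2126 + 228 × 0.0374 = 57.0 + 32.3 + 8.5 = 97.8.

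**5. Unnecessary pauses with an inert product.** The chance of firing by look 2 depends on the untreated rate. Section 6.1 itself gives 27% for patients over 65 and 16% to 30% for diabetes and heart disease or hypertension.

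- Group 3: 2.2% at 25%, 6.7% at 27%, 10.7% at 28%, 23.3% at 30%.
- Group 4: 2.7% at 14.8%. At 18.5%, which is 1.25 times the null and an assumption, 21.2%.

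**The case against.** An efficacy-only boundary is a legitimate design, and nothing in 6.3 overrides 8.7. The rate and its interval are reported at each interim, so the investigator would have them and could close the study on them. A reader might infer that the plan obliges enrolment to run to 228 or 219 in the face of harm. The documents do not support that. What stands is that 8.7 is discretionary, sets no threshold, rests with an investigator who is also the sponsor (Section 7.1.2), and refers to the interim analysis only for efficacy.

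A reader might also infer that all the transfusion risks named in Section 1.5 would surface as a raised progression rate. That goes too far. The protocol puts TRALI at about 1 in 12,000 transfusions, or 76/12,000 = 0.006 expected cases per Group 3 stage. TACO (under 1% to 8%), TRALI and anaphylaxis receive special consideration in Section 7.2 case by case, well before a 76-patient look. Section 7.1.2, read alone, sends every serious event to the IRB within 24 hours, although 7.2 then narrows reporting to events judged related. The argument rests on excess progression attributed to COVID-19, for which enhancement is the named mechanism; the protocol does not expect it to occur.

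Finally, an interval above the null need not mean harm. Without a control arm it may mean only that the historical rate is too low, and step 5 shows how readily that could happen. This objection stands in full, and it determines the form of the fix.

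**Conclusion.** The gap is real but limited. The statistical rule never requires a review when the data point the wrong way, although the limit that would show it is already computed. The 98-of-228 comparison is a ceiling on the benefit: it assumes a true rate of 40%, which no section gives, that every review ends enrolment, and that 8.7 would otherwise go unused. At 30% the ceiling is 201 of 228. The low pause rates of 2.2% and 2.7% hold only if the null rates are exactly right; within the plan's own figures for Group 3 the rate reaches 23%. Together these support a trigger for review, not a stopping rule. A badly wrong null would itself be worth knowing before the next stage opens, since every efficacy conclusion depends on it. No error in power or type I error is claimed.

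**What to change.** Add to Section 6.3, with a cross-reference in Section 8.7: if at an interim the lower limit of the same score interval exceeds the null proportion (at least 28/76 or 51/152 in Group 3; at least 18/73 or 32/146 in Group 4), the next stage for that group does not open automatically until the result has been reviewed, including whether the historical null is wrong. State that the trigger is non-binding for type I error. The sponsor should name who carries out the review and specify what may follow.

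The cost is one sentence and no new computation, sample size, power or alpha. The price is the occasional unnecessary pause quantified in step 5, which should be stated beside the rule so that a pause is not taken as a finding of harm. If the null rates are revised under the last paragraph of 6.3, the trigger counts must be recalculated.

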1.2 Clinical Characteristics of COVID-19 Disease

In the largest published review from Wuhan China, 1099 patients were followed with confirmed COVID-19 infection. A primary composite end-point event occurred in 67 patients (6.1%), including 5% who were admitted to the ICU, 2.3% who underwent invasive mechanical ventilation, and 1.4% who died. The majority of patients (58%) received intravenous antibiotic therapy and oxygen was administered in 41.3% of patients. CT radiograph was performed on 975 patients and it showed ground-glass opacities in 56.4%, local patchy shadowing in 41.9% and bilateral patchy shadowing in 51.8% and interstitial abnormalities in 14.7%. Chest radiographs were performed in 274 patients and abnormalities were documented in 59.1% (20.1%, 28.1%, 36.5% and 4.4%; respectively). In severe cases, radiographic abnormalities were seen on CT study in 94.6% of patients. For hospitalized patients, fever was present in 88.1% of non-severe and 91.9% of severe patients.

A total of 173 patients were classified as having severe disease per the guidelines of the American Thoracic Society guidelines. For those 926 that presented with non-severe disease, 35.7% required oxygen, 2.4% required ICU admission and none required mechanical ventilation. For those with severe disease, 71.1% required oxygen therapy, 19.1% were admitted to the ICU and 38.7% required mechanical ventilation. The median length of hospital stay for the non-severe was 11 days (10-13) and for the severe 13 days (11.5-17). Death occurred in 0.1% of the patients with non-severe disease and 8.1% of patients with severe disease. For patients presenting with severe disease 71.1% required oxygen therapy, 15.6% developed acute respiratory distress syndrome, admission to the ICU was 19.1%, 38.7 percent required mechanical ventilation (14.5% invasive and 32.4% noninvasive) and median hospital duration was 13 days.

Correlate laboratory studies included C-reactive protein that was elevated above 10 mg/L in 81.5% of those with severe disease and in 56.4% with non-severe disease. Procalcitonin

greater than 0.5 ng/mL was seen in only 3.7% of those with non-severe disease and 13.7% with severe disease presentation.

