3.1.1 Primary and Secondary Endpoints and Efficacy Assessments

The primary endpoint of the study will be:

- 1) progression to severe disease for those with high-risk disease that present with mild/non-severe disease, and
- 2) progression to severe disease for health care workers who present with asymptomatic, mild or non-severe disease.

Secondary endpoints will include:

- 1) Acute care facility/hospital length of stay
- 2) Number of days requiring oxygen support
- 3) Number of days in an intensive care unit
- 4) Number of days on mechanical ventilation (invasive, noninvasive and ECMO)
- 5) Incidence of viral disease associated cardiomyopathy
- 6) Incidence of multi-organ dysfunction/failure
- 7) Safety of transfusion—Incidence of severe adverse events

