6.2 Secondary Endpoints

6.2.1

Secondary endpoints will be analyzed for potential efficacy and statistically compared to historical or matched controlled comparison population. For patients with severe disease, the expected rate of ICU admission is 19.%, with 38.7% requiring mechanical ventilation (14.5% invasive), 94.6% had radiographic abnormalities of the chest, 15.6% developing acute respiratory distress syndrome, and median hospital stay of 13 days. A total of 14% of patients with COVID-19 disease developed severe disease.

6.2.2

Impact of donor sera neutralizing antibody titer will be correlated to clinical outcome.

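### The plan promises a statistical comparison of its secondary endpoints, but its only two-sample method (6.3) cannot analyse the four day-count endpoints, and the benchmarks in 6.2.1 describe severe disease, which the trial does not enrol

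*Combined protocol and SAP*

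**What the plan says.** Section 3.1.1 lists seven secondary endpoints. The first four are durations, among them "Acute care facility/hospital length of stay", "Number of days requiring oxygen support" and "Number of days in an intensive care unit"; the fourth is days on mechanical ventilation. The other three are incidences (cardiomyopathy, multi-organ failure, severe adverse events).

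Section 6.2.1 states the intent: "Secondary endpoints will be analyzed for potential efficacy and statistically compared to historical or matched controlled comparison population". It names no test, and no source or matching method for the controls. Its benchmarks are introduced as those of patients with severe disease: 19% admitted to ICU, 38.7% ventilated and a median hospital stay of 13 days.

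Section 6.3 says that, once the trial is complete, "we will conduct secondary analysis to compare outcomes of this trial with published historical experience". The method follows: "We will use the score test for comparing two proportions in each evaluation", and "We will report both p value and 95% score confidence interval for difference between two proportions".

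For the 926 patients with non-severe disease, section 1.2 reports that "35.7% required oxygen, 2.4% required ICU admission and none required mechanical ventilation", with a median hospital stay of 11 days.

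**The concern.** A score test for two proportions needs a count of patients with an event and a denominator in each sample. A number of days is neither, and the plan gives no rule for turning days into yes or no. No rank, count or time-to-event method is named.

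The comparator side has its own gap. For oxygen, ICU and ventilation the documents hold only percentages of patients, so naming a test for durations would still leave nothing published in the documents to compare with. Hospital stay is the exception: medians in days are given, but a two-proportion test cannot use a median. Those medians are also hospital stays, whereas a participant who is never admitted has zero days.

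The Protocol Summary and section 2.1 make the clinical course, expressed largely in days, the secondary objective for both groups. With no fixed method, the analyst would have to choose a cut-point, a test or a control set after seeing the data. In a single-arm study judged against history, that choice can decide the result.

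**Working it through.** **1. The plan's own figures.** No power or sample size is stated for any secondary endpoint. The primary sizes in 6.1 do reproduce. They use n = (1.960 + 0.842)² p0(1 − p0)/(p0 − p1)², times 1.165 for three Pocock looks at critical value 2.289, rounded up per stage.
- Group 3 (25% to 16.3%): 194.4 × 1.165 = 226.5, so 3 × 76 = 228; expected enrolment 159.6 (plan: 159).
- Group 4 (14.8% to 7.5%): 185.7 × 1.165 = 216.4, so 3 × 73 = 219; expected enrolment 153.0 (plan: 152).

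These supply the trial sample sizes used below.

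**2. Endpoint, test and comparator side by side.**

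| Endpoint (3.1.1) | Type | Score test for two proportions applies? | Comparator, non-severe (1.2) | Comparator, severe (6.2.1; oxygen from 1.2) |
|---|---|---|---|---|
| Hospital stay | days | no | median 11 days | median 13 days |
| Oxygen | days | no | 35.7% of patients | 71.1% of patients |
| ICU | days | no | 2.4% of patients | 19% of patients |
| Ventilation | days | no | 0% of patients | 38.7% of patients |
| Three incidences | proportion | yes | – | – |

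Four of the seven endpoints cannot enter the named test. For three of those four, no comparator in days appears anywhere in the documents.

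**3. The 6.2.1 benchmarks.** Groups 3 and 4 enrol asymptomatic, mild or non-severe patients. Suppose plasma did nothing and ICU use equalled the non-severe 2.4%. A comparison with 19% would still show a difference of 19 − 2.4 = 16.6 percentage points. If the severe figures are meant only for participants who progress, the comparison falls on a subset defined after treatment. At the target rate that is 0.163 × 228 ≈ 37 patients in Group 3.

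**4. What a yes/no form could show.** Assume the 926 non-severe patients are the comparator and the test is two-sided at 5%. With n trial patients, p̄ the pooled proportion and Φ the normal distribution function:

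power = Φ{(|p1 − p2| − 1.96·s0)/s1}, where s0² = p̄(1 − p̄)(1/n + 1/926) and s1² = p1(1 − p1)/n + p2(1 − p2)/926.

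Any oxygen, 25% v 35.7% (a relative fall of 1 − 25/35.7 = 30%):

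| n | s0 | s1 | Power |
|---|---|---|---|
| 228 (Group 3 maximum) | 0.0349 | 0.0327 | 0.88 |
| 159 (Group 3 expected) | 0.0407 | 0.0378 | 0.76 |
| 152 (Group 4 expected) | 0.0415 | 0.0385 | 0.75 |
| 76 (Group 3 stop at stage 1) | 0.0569 | 0.0521 | 0.47 |

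For n = 228: (0.107 − 1.96 × 0.0349)/0.0327 = 1.18, and Φ(1.18) = 0.88. With a 35% relative fall, as Group 3 assumes for its primary endpoint, power is 0.88 at 152 and 0.96 at 228.

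Any ICU: expected events at 2.4% are 0.024 × 228 = 5.5. A 35% relative reduction gives 0.65 × 2.4% = 1.56%. Power is 0.09 at 228 and 0.06 at 152. Halving the rate gives 0.15 at 228.

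Any ventilation: the comparator is 0 of 926, so no reduction can be shown at any sample size.

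**The case against.** The strongest defence is that 6.3 does not govern these endpoints. It speaks of a secondary analysis of trial outcomes, follows directly on the one-sample analysis of the progression rate, and uses the word evaluation for that rate comparison. The score test suits a two-sample comparison of progression rates. This reading is tenable. A reader might infer that the plan definitely prescribes a wrong test for durations, and the text does not settle that. The gap remains, however: section 6.2, which would then stand alone, promises a statistical comparison and names no method.

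Second, 6.2.1 also allows matched controls, who could supply day counts. That stands, so it would be too strong to say that durations can never be compared. But no source, matching method or test is given, and 6.3 mentions only published experience.

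Third, a reader might infer that recoding days to yes/no rescues oxygen, ICU and ventilation alike. It does not: ICU power is about 9% and the ventilation comparator is zero. Only oxygen gives a usable test, and it measures need rather than duration.

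Fourth, the 926 patients are not a close match. They were not selected as high-risk, as Group 3 is, and they are not asymptomatic staff, whom Group 4 admits. This stands and limits any p value to exploratory use.

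Finally, these are secondary comparisons in a single-arm Phase II study, and descriptive reporting is always open to the sponsor. That is correct, and it limits the weight of the point.

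**Conclusion.** The point holds in this form: four of the seven secondary endpoints in 3.1.1, in both groups, have either an inapplicable test or no stated method, depending on how 6.3 is read. Either way the promise in 6.2.1 cannot be carried out as written. For oxygen, ICU and ventilation there is also no published comparator in days, and the benchmarks placed in 6.2.1 belong to a severity that the trial does not enrol.

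The mismatch itself rests on the text alone. The power figures rest on assumptions: that the non-severe cohort in 1.2 is the comparator, that its severity classification and follow-up are close enough to this trial's, that the test is two-sided at 5%, and that oxygen use falls to 25%. The 88% applies only at Group 3's maximum; 75-76% at expected enrolment is the fairer summary.

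Nothing here touches the primary test, the stopping rule or the sample size. It should be corrected before analysis, but it does not threaten the trial's main conclusion.

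**What to change.** Amend 3.1.1, 6.2.1 and 6.3 as follows.

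- Restrict the two-proportion score test to proportions, and say which endpoints it covers.
- Add any oxygen support by Day 30 as the tested form of the oxygen endpoint, against 35.7% of 926 (section 1.2) in place of severe-disease figures. Label it exploratory, because that cohort was selected neither as high-risk nor as asymptomatic.
- Report any ICU admission and any mechanical ventilation as proportions with score intervals and no efficacy test, showing 2.4% and 0% for context.
- Report all day counts as medians with quartiles and no p value against published history. Count never-admitted patients as zero days in length of stay. Treat the days with pneumonia and fever and the days to viral clearance named in section 2.1 in the same way.
- Either delete the matched-control option or specify its source, matching method and test in advance.

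The cost is mainly wording. ICU, ventilator and hospital days are already recorded under 5.1.3.3. Oxygen days are an endpoint but are not in that list, so their collection should be confirmed there. No patients or visits are added. The downside is that durations are not tested against published history, and the yes/no form shows whether oxygen was needed, not for how long.

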In a larger report from Chinese Center for Disease Control and Prevention of 72,314 cases 14% presented with severe disease that was defined as dyspnea, respiratory frequency \geq 30, blood oxygen saturation \leq 93%, partial pressure of arterial oxygen to fraction of inspired oxygen ratio < 300, and/or lung infiltrates >50% within 24-48 hours.** Critical disease developed in 5% that resulted in respiratory failure, septic shock and/or multi-organ failure. In this report the case fatality rate (CFR) was 8.0% in patients age 70-79, 14.8% in patients over age 80, and 49% in critical cases. CFR was elevated among those with preexisting comorbid conditions: 10.5% for cardiovascular disease, 7.3% for diabetes, 6.3% for chronic respiratory disease, 6.0% for hypertension and 5.6% for cancer. A total of 1,716 infected were health care workers. Overall, 14.8% of health care workers developed severe or critical disease, and 5 deaths were observed.**

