3.2 Number of Patients

The number of patients expected per each of the 2 groups:

Group 3: High Risk: n=159
Group 4: Health Care Providers: n=152

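### For rare yes/no outcomes such as death, the score test that Section 6.3 requires in every comparison with published data signals harm too readily

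*Combined protocol and SAP*

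**What the plan says.** Section 6.3 separates the primary analysis from a later one. The primary analysis sets a one-sample score interval, with critical value 2.289, against the null rate. Then: "After completing the trial, we will conduct secondary analysis to compare outcomes of this trial with published historical experience". The method follows: "We will use the score test for comparing two proportions in each evaluation", and "We will report both p value and 95% score confidence interval for difference between two proportions". There is no minimum expected count and no exact alternative, and neither the comparator cohorts nor the type of score interval is named. Section 6.2.1 also says that secondary endpoints will be tested against a historical or matched population.

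Some of these outcomes are rare in people who enter without severe disease. Section 2.1 lists death as a secondary objective for Group 3, and Section 3.1.1 lists incidence of cardiomyopathy and of multi-organ failure. The nearest published figures are in Section 1.2: "Death occurred in 0.1% of the patients with non-severe disease and 8.1% of patients with severe disease"; "For those 926 that presented with non-severe disease, 35.7% required oxygen, 2.4% required ICU admission and none required mechanical ventilation"; and, among 1,716 infected health care workers, "Overall, 14.8% of health care workers developed severe or critical disease, and 5 deaths were observed".

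The expected trial sizes in Section 3.2 are "Group 3: High Risk: n=159" and "Group 4: Health Care Providers: n=152". The table in Section 6.1 gives maxima of 228 and 219, in stages of 76 and 73.

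**The concern.** The score test relies on a normal approximation to the difference in proportions. With about 0.2 expected events in the trial group and a comparator several times larger, the statistic is strongly skewed: zero events can never be significant, while one or two chance events can lie far out in the upper tail. The approximation then puts the whole error rate on the harm side.

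The trial has a single arm, so published figures are the only context for its deaths. A p value below 0.05 for excess mortality, resting on one or two deaths, could be read as a safety signal. Changing to an exact method after seeing that result would look post hoc.

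**Working it through.** **Trial sizes.** These reproduce. With null variance and a three-look Pocock boundary of 2.289 (overall two-sided alpha 0.050), n = D × p0(1 − p0)/(p0 − p1)², where D is the squared drift for 80% power, about 9.13.

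- Group 3: 0.25 × 0.75/0.087² = 24.77, giving 226.3, so 76 per stage, maximum 228, expected 158.9.
- Group 4: 0.148 × 0.852/0.073² = 23.66, giving 216.1, so 73 per stage, maximum 219, expected 151.8.

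The Group 3 text in Section 6.1 gives a maximum of 219 and the overview an expected 152. The calculation supports the table's 228 and 159, which I use.

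**Comparators (assumed).** Deaths in non-severe patients: 0.1% of 926 = 0.93, taken as 1/926. Deaths in health care workers: 5/1,716 (0.29%). The p value is taken as two-sided.

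**Score test.** z = (x1/n1 − x2/n2)/√[p(1 − p)(1/n1 + 1/n2)], with p = (x1 + x2)/(n1 + n2).

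- 1/76 against 1/926: p = 2/1,002 = 0.001996; difference 0.01316 − 0.00108 = 0.01208; standard error √(0.001992 × 0.01424) = 0.00533; z = 2.27.
- 2/159 against 1/926: p = 3/1,085 = 0.002765; difference 0.01150; standard error √(0.002757 × 0.00737) = 0.00451; z = 2.55.

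**Fisher check for the first table.** Two deaths among 1,002 patients put at least one in the 76 with probability 1 − (926 × 925)/(1,002 × 1,001) = 0.146.

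The exact unconditional test below uses |z| and maximises over the common rate.

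| Deaths | Score p | Fisher p | Exact unconditional p |
|---|---|---|---|
| 1/76 v 1/926 | 0.023 | 0.146 | 0.069 |
| 1/159 v 1/926 | 0.157 | 0.272 | 0.161 |
| 2/159 v 1/926 | 0.011 | 0.058 | 0.023 |
| 2/228 v 1/926 | 0.041 | 0.101 | 0.045 |
| 1/152 v 5/1,716 | 0.44 | 0.40 | 0.57 |
| 2/152 v 5/1,716 | 0.048 | 0.105 | 0.074 |

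One death against 1/926 is significant by the score test only for n up to 96, so only at the first stage. At a true rate of 0.1%, the chance of at least one death in 76 is 1 − 0.999^76 = 7.3%.

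**Error rate.** I summed the product of two binomial probabilities with equal true rates over all tables with |z| > 1.96. Up to a rate of 0.5% every rejection is in the harm direction, so each figure is both the total size and the harm-tail size. At 1% a benefit tail of at most 0.3% appears at the maximum sizes.

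| n1 v n2 | 0.1% | 0.2% | 0.3% | 0.5% | 1% |
|---|---|---|---|---|---|
| 76 v 926 | 5.65% | 6.87% | 6.35% | 5.44% | 4.73% |
| 159 v 926 | 6.43% | 6.66% | 6.27% | 5.32% | 4.01% |
| 228 v 926 | 8.92% | 8.31% | 6.63% | 4.39% | 3.68% |
| 73 v 1,716 | 6.39% | 7.92% | 6.35% | 5.19% | 4.40% |
| 152 v 1,716 | 7.41% | 6.53% | 6.01% | 5.30% | 4.06% |
| 219 v 1,716 | 5.05% | 5.27% | 5.18% | 4.38% | 3.69% |

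For rates of 0.1% to 0.3%, Fisher's harm-tail rate in the same six settings is 0.3% to 1.9%.

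**The case against.** **One event is not generally enough.** A reader might infer that any single event becomes significant. For death this fails at the expected sizes (p = 0.157 and 0.44). It fails even at Group 4's first stage, where 1/73 against 5/1,716 gives p = 0.119.

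**Ventilation.** The starkest case would be one ventilated patient against 0/926: 1/159 gives score p = 0.016 and Fisher 0.147. The protocol lists ventilation as days, however, so this applies only if it is analysed as yes/no. Even then the interval result depends on an unnamed method: for 1/159 the Miettinen-Nurminen interval (about 0.1% to 3.5%) excludes zero and the Newcombe interval (−0.03% to 3.5%) does not.

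**The comparators fit poorly.** The 926 are all non-severe patients, whereas Group 3 is high risk. If 25% progressed (Section 6.1) and progressors died at the 8.1% given for severe disease, mortality would be about 2%, not 0.1%. That is also an assumption, but it makes a shared rate of 0.1% doubtful for Group 3. An exact test does not cure this: with true rates of 2% against 0.1%, Fisher rejects in 45% (n = 76) to 84% (n = 228) of trials. The rates that Section 6.2.1 prints are mostly for severe disease and are not rare. No non-severe rate is given for multi-organ failure or cardiomyopathy, so no failure is shown for them. Death is not on Group 4's list of secondary objectives.

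**Exact tests differ.** In the two Group 3 tables with two deaths, the unconditional test also falls below 0.05. With 2/73 against 5/1,716, Fisher rejects as well (0.030).

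All of this stands, and it narrows the point. It leaves untouched that the plan requires this test without exception, including where its harm-side error is at least double the nominal 2.5%.

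**Conclusion.** The point holds in a limited form, as a minor one. For rare yes/no outcomes, above all death, the required score test rejects in about 5% to 9% of trials when both true rates are 0.1% to 0.3%, always towards harm, against a nominal 2.5% on that side. This rests on the Section 1.2 comparators, a two-sided p value and equal true rates. At about 0.5% to 1% or more, total size is near or below 5%, although most of it still lies on the harm side.

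A reader might infer that the trial's main conclusion is at risk. The documents do not support that: the primary test, stopping rule and sample size use the one-sample comparison with 25% and 14.8%, and no decision rule is attached to the secondary comparisons.

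**What to change.** Keep the score test for common outcomes and add one sentence to Section 6.3, for example:

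> *Where the number of events expected in the trial group at the pooled rate, n1(x1 + x2)/(n1 + n2), is below 5, an exact test and a matching exact confidence interval for the difference replace the score test and score interval.*

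In the six death tables above this count is 0.15 to 0.59, so all would be covered. The sentence should name one test in advance, because the choice can change the result. Fisher keeps the harm tail below 2.5% at rates of 0.1% to 0.3%. The unconditional test is less conservative, but in the two-sided form used here it controls only the total at 5%. Naming the comparator cohort and denominator for each outcome, and the type of score interval kept for common outcomes, would help, since no choice of test repairs a mismatched comparator.

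No new data are needed. The cost is sensitivity: exact tests are conservative, Fisher most of all, so a real difference in a rare outcome may need one or two more events to reach p < 0.05. The threshold of 5 also takes in rates where the score test's total size is acceptable (at n = 159, pooled rates up to 5/159 = 3.1%).
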